8.3.8 Screen Failures and Rescreening

Screen failures are defined as participants who consent to take part in the clinical study but are not subsequently randomized. A minimal set of screen failure information is required to ensure transparent reporting of screen failure participants, to meet the Consolidated Standards of Reporting Trials (CONSORT) publishing requirements, and to respond to queries from regulatory authorities. Minimal information includes date of consent, demography, screen failure details, eligibility criteria, and any serious AEs (SAEs).

8.3.8.1 Retesting During Screening

Laboratory parameters and/or assessments that are included in the Screening procedures ([Table 1 in Section 1](#)) may be repeated during the Screening Period in an effort to find all possible qualified participants. Consultation with the medical monitor may be needed to identify whether repeat testing of any particular parameter is clinically relevant.

The most current result prior to randomization is the value by which study inclusion will be assessed, as it represents the participant's most current clinical state.

8.3.8.2 Rescreening

This study will permit the rescreening of a participant who has discontinued the study as a pre-treatment failure (i.e., the participant has not been randomized/has not been treated). Consultation with the medical monitor may be needed to identify whether rescreening is clinically relevant. If rescreened, the participant must sign a new ICF.

In the event that histologic evaluation of the biopsy of an otherwise qualified participant results in a diagnosis of NASH with cirrhosis, that individual is not eligible for the present study (MB130-068) but may be considered for enrollment under protocol MB130-069 (A

Phase 2b Randomized, Double-Blind, Placebo-Controlled Study Evaluating the Safety and Efficacy of BMS-986036 (PEG-FGF21) in Adults with Nonalcoholic Steatohepatitis [NASH] and Compensated Liver Cirrhosis). Laboratory parameters and/or assessments that were collected as Screening procedures for this study (MB130-068; [Table 1](#) in [Section 1](#)) may be utilized for the same purpose for MB130-069.

Conversely, in the event that histologic evaluation of the biopsy of an otherwise qualified participant for MB130-069 results in a diagnosis of NASH with stage 3 liver fibrosis, that individual is not eligible for the MB130-069 study but can be considered for enrollment under the present study (MB130-068). Laboratory parameters and/or assessments that were collected as Screening procedures for MB130-069 may be utilized for the same purpose (Table 1 in Section 1) in this study (MB130-068).

For participants who are rescreened, consult with the medical monitor to confirm which parameters and/or assessments that were collected as part of the original Screening Period procedures may be utilized.

8.3.9 Withdrawal of Participants

8.3.9.1 Discontinuation of Study Medication

Participants MUST discontinue investigational product (IP) (and non-investigational product [non-IP] at the discretion of the investigator) for any of the following reasons.

- Participant's request to stop study medication. Participants who request to discontinue study medication will be expected to complete an ET Visit and subsequent follow-up visits/procedures per the Schedule of Activities (e.g., Week 52/PTFU; Section 1). The only exception to this is when a participant specifically withdraws consent for any further contact with him/her or persons previously authorized by participant to provide this information. Participants' withdrawal of consent should be explained in detail in the medical records by the investigator as to whether the withdrawal is from further treatment with study medication only or also from study procedures and/or ET, Week 52/PTFU Visit, etc. (see [Section 8.3.9.2](#))
- Any clinical AE, laboratory abnormality or intercurrent illness, which, in the opinion of the investigator, indicates that continued participation in the study is not in the best interest of the participant
- The participant experiences a major bone fracture or is diagnosed with osteoporosis that requires treatment
- Abnormal liver tests as defined in [Section 8.5.3.1](#)
- On 2 consecutive visits (at least 2 weeks apart), a participant has an eGFR < 30 mL/min/1.73 m², according to the *Modification of Diet in Renal Disease Study* equation
- If there is a significant protocol violation. The violation should be discussed with the medical monitor prior to discontinuing study medication
- Loss of ability to freely provide consent through imprisonment or involuntary incarceration for treatment of either a psychiatric or physical (e.g., infectious disease)

illness (Note: Under specific circumstances, a participant who has been imprisoned may be permitted to continue as a participant. Strict conditions apply, and sponsor approval is required.)

- The participant becomes pregnant (study medication must be discontinued immediately)
In the case of pregnancy (see [Section 8.5.3.1](#)), the investigator must immediately notify the medical monitor or designee of this event. In the event a participant becomes pregnant during a clinical study, the study medication must be discontinued immediately. In most cases, the study medication will be permanently discontinued in an appropriate manner. The medical monitor should be contacted within 24 hours of awareness of the pregnancy
- Termination of the study or program by the sponsor
- If a participant loses more than 10% of their total body weight, the investigator should contact the medical monitor. The investigator, together with the medical monitor, will then determine whether the participant should continue to take study medication

If study medication is discontinued prior to the participant's completion of the study, the reason for the discontinuation must be documented in the participant's medical records and entered on the appropriate eCRF page. The discontinuation should also be reported via the IRT. As indicated, appropriate follow-up and/or alternate medical care must be arranged for the participant. Please notify the medical monitor as soon as possible when discontinuation of study medication is being considered.

See [Section 8.4.6](#) for details regarding dose modification and/or treatment interruption.

Participants who prematurely discontinue study medication will be expected to complete an ET Visit and subsequent follow-up visits/procedures per the Schedule of Activities, including a Week 52/PTFU Visit ([Table 2](#) in [Section 1](#)), DXA and Immunogenicity Follow-Up Visits ([Table 3](#) in [Section 1](#)) (see [Section 8.5.3.6](#)). The only exception to this requirement is when consent is withdrawn for all study procedures or the participant loses the ability to consent freely (i.e., is imprisoned or involuntarily incarcerated for the treatment of either a psychiatric or physical illness). Participants who discontinue study medication will not be replaced (see [Section 8.3.9.4](#)).

8.3.9.2 Discontinuation from Study Participation

When a participant (or caregiver as applicable) requests to discontinue study participation, the participant will undergo an ET Visit as described in Table 2 in Section 1.

The only exception to this requirement is when consent is withdrawn for all study procedures or the participant loses the ability to consent freely (e.g., is imprisoned or involuntarily incarcerated for the treatment of either a psychiatric or physical illness).

Expectations are as follows:

- Participants should notify the investigator of the decision to withdraw consent from future follow-up **in writing**, whenever possible

- The withdrawal of consent should be explained in detail in the medical records by the investigator, as to whether the withdrawal is from further treatment with study medication only (see [Section 8.3.9.1](#)), or also from study procedures and/or Week 52/PTFU (see [Section 1](#)), and entered on the appropriate eCRF page
- In the event that vital status (whether the participant is alive or dead) is being measured, publicly available information should be used to determine vital status only as appropriately directed in accordance with local law
- If the participant withdraws consent for disclosure of future information, the sponsor may retain and continue to use any data collected before such a withdrawal of consent

The following procedures must be followed upon participant withdrawal:

- Assessments for the ET Visit must be performed, provided that the participant has not withdrawn consent for these activities
- All required eCRF pages must be completed, including the date of and explanation for the withdrawal
- As indicated, appropriate follow-up and/or alternate medical care must be arranged for the participant outside of sponsor responsibility
- Participants who discontinue from study participation (yet have not withdrawn consent) may decline further study visits, however, they will be offered additional visits for the purpose of BMD assessment (see [Section 8.5.3.8](#)) and immunogenicity testing (see [Section 8.5.3.6](#))

8.3.9.3 Lost to Follow-Up

- All reasonable efforts must be made to locate participants to determine and report their ongoing status. This includes follow-up with persons authorized by the participant
- Lost to follow-up is defined by the inability to reach the participant after a minimum of 3 documented phone calls, faxes, or emails as well as lack of response by participant to one registered mail letter. All attempts should be documented in the participant's medical records
- If it is determined that the participant has died, the site will use permissible local methods to obtain date and cause of death
- If investigator's use of third-party representative to assist in the follow-up portion of the study has been included in the participant's informed consent, then the investigator may use a sponsor-retained third-party representative to assist site staff with obtaining participant's contact information or other public vital status data necessary to complete the follow-up portion of the study
- The site staff and representative will consult publicly available sources, such as public health registries and databases to obtain updated contact information
- If, after all attempts, the participant remains lost to follow-up, then the last known alive date as determined by the investigator should be reported and documented in the participant's medical records

8.3.9.4 Replacement of Participants

Participants who discontinue from study medication or from study after randomization will not be replaced. Participants who discontinue participation in the study after randomization will not be allowed to reenroll.

8.4 Treatment

Study medication is defined as any investigational treatment(s), marketed product(s), placebo or medical device intended to be administered to a study participant according to the study randomization or treatment allocation.

Each study medication must be listed as either an IP or non-IP.

Study treatment includes both IP and non-IP and can consist of the following:

- All products, active or placebo, being tested or used as a comparator in a clinical study
- Study required premedication
- Other drugs administered as part of the study that are critical to claims of efficacy (e.g., background therapy, rescue medications)
- If specific criteria are required for treatment in a given phase of the study (e.g., extension phase), provide detailed criteria in this section
- Diagnostic agents: (such as glucose for glucose challenge) given as part of the protocol requirements must also be included in the dosing data collection.

An IP, also known as investigational medicinal product in some regions, is defined as a pharmaceutical form of an active substance or placebo being tested or used as a reference in a clinical study, including products already with a marketing authorization but used or assembled (formulated or packaged) differently than the authorized form, or used for an unauthorized indication, or when used to gain further information about the authorized form.

Study medication includes both BMS-986036 and placebo and is described in [Table 5](#) below.

Other medications used as support or escape medication for preventative, diagnostic, or therapeutic reasons, as components of the standard of care for a given diagnosis, may be considered as non-IPs.

Table 5 Study Medications

Product	Potency	IP/Non-IP	Blinded or Open Label	Packaging/Appearance	Storage Conditions (per Label)
BMS-986036	10 mg/mL	IP	Blinded	Pre-Filled Syringe	Refer to the label on the container
BMS-986036	20 mg/mL	IP	Blinded	Pre-Filled Syringe	Refer to the label on the container
Placebo	0 mg/mL	IP	Blinded	Pre-Filled Syringe	Refer to the label on the container

IP = investigational product; non-IP = non-investigational product

8.4.1 Treatments Administered

The investigator must ensure that the IP will be used only in accordance with the protocol. The study medication doses, dosing frequency and route of administration for each participant are shown in Table 6 below.

Table 6 Study Medication Doses, Dosing Frequency, and Route of Administration

Study Treatment	Unit Dose Strength(s)/Dosage Level(s)	Dosage formulation Frequency of Administration	Route of Administration
BMS-986036 10 mg arm	1 mL/10 mg/mL BMS-986036	Once weekly	Subcutaneous
	1 mL placebo		
BMS-986036 20 mg arm	1 mL/20 mg/mL BMS-986036	Once weekly	Subcutaneous
	1 mL placebo		
BMS-986036 40 mg arm	2 × 1 mL/20 mg/mL BMS-986036	Once weekly	Subcutaneous
Placebo	2 × 1 mL placebo	Once weekly	Subcutaneous

8.4.2 Study Medication Administration

Participants should be instructed to make every effort to administer study medication on the same day each week at approximately the same time of day. Each weekly administration will consist of 2 SC injections.

On Day 1 and at the Week 4, 8, 12, 16, 20, 24, 32, and 40 Visits, study medication will be self-administered by the participant or administered by their designee at the study site as part of the participant's scheduled study visits. At those visits, study medication dosing should be held until all study-related assessments, including participant questionnaires, vital signs, ECG, AE evaluation, physical examinations, and laboratory sample collection (including trough [predose] PK) have been completed. [REDACTED]

[REDACTED] If a study visit occurs on a day that is not a planned dosing day, the participant should continue to administer the medication on the planned dosing day; all study-related assessments will continue to be performed at the planned study visit (in-clinic administration of study drug would not occur). [REDACTED]

[REDACTED]

Study medication is blinded and is supplied in a pre-filled syringe. Each participant will be dispensed a treatment kit containing 2 smaller boxes (for each weekly administration). Each smaller box will contain 1 pre-filled syringe of the medication. Both syringes will be administered in the abdominal area at different locations per training guidelines. Study medication will be assigned by the IRT system.

Guidance and training on administration should be given to the participant (or caregiver, if applicable) prior to the first administration. At a minimum, the first administration should be done by the participant under the supervision of qualified site personnel. Training may be repeated as necessary at any study visit at the discretion of the investigator to maintain treatment compliance. When injections are administered at the site during study visits, site staff may observe the injection to ensure proper technique is being employed. Participants will be required to capture the date, time, and location of each injection on the supplied study medication administration card.

Specific instructions for study medication administration as well as training materials for participants (or caregivers, if applicable) are in the Pharmacy Manual.

8.4.3 Method of Treatment Assignment

After receiving the signed ICF but before any other study-related procedures are performed, the investigative site will access the enrollment option of the IRT system for assignment of a participant number (including participants not subsequently randomized or treated). This number is assigned sequentially by the system and will be unique across all sites. If a potential participant is rescreened, a new identification number will be used.

Randomization will be conducted in the following manner:

- Eligible participants will be randomized by the IRT using a prespecified schedule in a double-blind manner to 10 mg BMS-986036, 20 mg BMS-986036, 40 mg BMS-986036, or placebo arms in a 1:1:1:1 ratio based on the stratification factors specified in [Section 8.1](#)
- The IRT will provide study medication kit numbers that contain the appropriate study medication (BMS-986036 or placebo) for dispensation to that participant

At subsequent study visits as listed in the Schedule of Activities ([Section 1](#)), the investigator or designee will access the IRT to receive the corresponding kit numbers assigned to the participant for the purpose of dispensing study medication.

8.4.4 Blinding of Study Medication

8.4.4.1 Maintaining the Blind

Blinded treatment assignments will be managed using the IRT. All syringes and syringe contents (BMS-986036 10 mg/mL, BMS-986036 20 mg/mL, and placebo) are identical in appearance. Investigative site staff, sponsor and designee personnel, and participants and their families will remain blinded to treatment assignments. Study medication will be administered in a double-dummy manner as described in [Section 8.4.2](#) in order to maintain the blind.

Sponsor and designee personnel may be unblinded once all participants have completed the Week 52/PTFU Visit and all data have been collected through that time point to facilitate analyses. Designated sponsor staff may be unblinded (obtain the randomization codes) prior to database lock to facilitate the bioanalytical analysis of PK samples and immunogenicity. A

bioanalytical scientist in the sponsor Bioanalytical Sciences department (or a designee in the external central bioanalytical laboratory) will be unblinded to (may obtain) the randomized treatment assignments in order to minimize unnecessary bioanalytical analysis of samples.

8.4.4.2 Circumstances for Unblinding

In the event of a medical emergency or pregnancy in an individual participant where knowledge of the study medication is critical to the participant's medical management, the blind for that participant may be broken by the investigator. The participant's safety takes priority over any other considerations in determining if a treatment assignment should be unblinded.

Before breaking the blind of an individual participant's treatment, the investigator should determine that the unblinded information is necessary (i.e., that it will alter the participant's immediate management). In many cases, particularly when the emergency is clearly not related to the IP, the problem may be properly managed by assuming that the participant is receiving active product. It is highly desirable that the decision to unblind treatment assignment be discussed with the medical monitor, but the investigator always has ultimate authority for the decision to unblind. The actual TASK of unblinding can be delegated by the investigator to a designee assigned the task on the Delegation of Authority. The principal investigator or appointed designee should only call in for emergency unblinding AFTER the decision to unblind the participant has been documented.

For this study, the method of unblinding for emergency purposes is through the IRT system. In case of an emergency, the investigator has unrestricted access to randomization information via IRT and is capable of breaking the blind through the IRT system without prior approval from the sponsor. After the unblinding, the investigator shall notify the medical monitor and/or study director. The method of unblinding for emergency purposes is described in the IRT Manual. Participant and unblinded treatment information and the reason for the blind being broken must be recorded on the appropriate study status page of the eCRF.

In cases of accidental unblinding, the site should contact the medical monitor and ensure every attempt is made to preserve the blind. Any request to unblind a participant for nonemergency purposes should be discussed with the medical monitor.

8.4.5 Study Medication Preparation, Handling, Storage, and Accountability

The IP should be stored in a secure area according to local regulations. It is the responsibility of the investigator to ensure that IP is dispensed only to study participants. The IP must be dispensed only from official study sites by authorized personnel according to local regulations.

The product should be stored in a refrigerator (2°C through 8°C [35.6°F through 46.4°F]) and protected from light. If concerns regarding the quality or appearance of the study medication arise, the study medication should not be dispensed, and the sponsor should be contacted immediately.

IP documentation must be maintained. This includes documentation of all processes required to ensure drug is accurately administered, drug storage, administration, and, as applicable, storage temperatures, and use of required processes.

Further details on accountability of study medication are in the Study Pharmacy Manual.

Further guidance and information on final disposition of unused and returned study medication and study supplies is provided in [Appendix 1](#).

8.4.6 Dose Modification

8.4.6.1 Modification of Dose

No dose reductions or modifications are allowed. If a participant interrupts treatment due to an AE, study medication may be restarted after consultation with the medical monitor.

8.4.6.2 Dose Interruption

If a participant has abnormal laboratory test result(s) and/or clinical AE(s) that, in the judgment of the investigator, could place the participant at risk, study medication administration should be interrupted, and the investigator should notify the medical monitor. Participants may receive further study medication when the AE or abnormal laboratory finding is resolved.

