8.5.1.1 Liver Biopsy

A liver biopsy will be performed during Screening if no liver biopsy specimen collected within 6 months (26 weeks) prior to informed consent is available and readable by the Central Pathologist.

The on-treatment liver biopsy should be performed within \pm 7 days of the Week 24 Visit. However, if a biopsy cannot be scheduled within the window specified above, the biopsy should be performed as close to schedule as possible.

For participants prematurely discontinuing study medication, liver biopsy will be performed at ET Visit if the participant has completed at least Week 20 and has not had a Week 24 biopsy. If a participant discontinues study participation prior to Week 20 they should consider having a liver biopsy at ET.

Histological assessment of the tissue sample will be conducted by a blinded Central Pathologist. The central reader will be a medical doctor, board certified in pathology, with experience in liver pathology in a clinical study setting.

The on-treatment liver biopsy results will remain blinded to site personnel until after the study database is locked; incidental findings of potential clinical relevance (as determined by the medical monitor) from the central pathologist will be provided to the investigator.

Any incidental findings of potential clinical relevance that are not directly associated with the objectives of the study should be evaluated and handled by the investigator per the site's standard of care and clinical judgment.

Liver tissue should be collected using a 16 gauge (or larger) cutting needle (e.g., Bard, Microvasive, or TruCut) whenever possible. Use of suction needles (e.g., Menghini, Jamshedi, or Klatskin) are allowed, but may cause fragmentation of fibrotic specimens and impede the evaluation of fibrosis, and should therefore be avoided, if possible. At least 2 cm length of tissue should be obtained.

Additional details on the acquisition, quality requirements, histological preparation, and shipping of histological samples are in the Central Laboratory Manual and the Central Pathology Manual.

Histological Scoring

NASH CRN

For associated primary and secondary endpoints, the NASH CRN system²⁶ will be used to score the histologic samples and results are reported as the NAFLD Activity Score (NAS) and the NASH CRN Fibrosis Score. The NASH CRN system is based on the concept that necroinflammatory lesions and stage of fibrosis should be evaluated separately; it assesses

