- Participants with elevated Baseline aminotransferase values experience additional increases greater than $2\times$ the Baseline (with concomitant elevations of total bilirubin $> 2\times$ ULN) **AND** ALT and/or AST is > 200 U/L.

If the new elevations in aminotransferases persist and the participant is symptomatic, then the drug should be discontinued, and the participant should be evaluated for other causes of liver injury or disease. The medical monitor should be contacted within 48-72 hours.

If the participant is asymptomatic, the participant should be placed under “close observation”, defined as physical examination and laboratory evaluation 2-3 times per week.

If close observation is not possible, study medication should be discontinued. The frequency of retesting can decrease to once a week or less if abnormalities stabilize or the study medication has been discontinued and the participant is asymptomatic.

Discontinuation or Temporary Interruption of Study Medication

In addition to the reasons for discontinuation described above, study medication should be discontinued or temporarily interrupted if either of the 2 following scenarios occur:

1) Aminotransferases (ALT and/or AST) $> 2\times$ Baseline and aminotransferases $> 3\times$ ULN **and** either:

- i. the increase is accompanied by a concomitant increase in total bilirubin to $> 2\times$ Baseline **OR** the INR concomitantly increases by > 0.2 ;

OR

- ii. there are concomitant signs and symptoms of new-onset fatigue, nausea, vomiting, right upper quadrant pain or tenderness, fever, rash, and/or eosinophilia ($> 5\%$).

2) Total bilirubin increases to $> 2\times$ ULN **AND**:

- i. there are concomitant signs and symptoms of new-onset fatigue, nausea, vomiting, right upper quadrant pain or tenderness, fever, rash, and/or eosinophilia ($> 5\%$).

If the above rule is met, a potential DILI work up for competing etiologies (e.g., alcohol use, viral hepatitis, biliary obstruction, autoimmune liver disease) must be performed, and a complete liver profile including INR must be repeated within 48-72 hours. **The medical monitor should be contacted within 48-72 hours.** Study medication can be restarted only if an alternative etiology is definitively identified and liver tests (aminotransferases, total bilirubin and/or INR) have returned to Baseline.

Other Safety Considerations

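### Protocol Sections 8.3.9.1, 8.4.6 and 8.5.3.1 do not agree on stopping and restarting study medication after abnormal liver tests, and no order of precedence is stated

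*Protocol*

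**What the plan says.** Four protocol passages bear on a participant whose liver tests become abnormal on treatment.

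- **Section 8.3.9.1** opens its list with "Participants MUST discontinue investigational product (IP" and includes "Abnormal liver tests as defined in" Section 8.5.3.1 among the reasons. It attaches no restart provision to that reason and expects an ET Visit. It also sends the reader to Section 8.4.6 "for details regarding dose modification and/or treatment interruption".
- **Section 8.5.3.1**, under its heading on discontinuation or temporary interruption, says "study medication should be discontinued or temporarily interrupted if either of the 2 following scenarios occur". It then says "Study medication can be restarted only if an alternative etiology is definitively identified" and adds a second condition, that the liver tests have returned to Baseline.
- **Section 8.4.6.2** covers any abnormal laboratory result or clinical adverse event (AE) that the investigator judges to be a risk. Dosing is interrupted, the medical monitor is notified, and "Participants may receive further study medication when the AE or abnormal laboratory finding is resolved".
- **Section 8.4.6.1** says that after an interruption for an AE "study medication may be restarted after consultation with the medical monitor".

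The visit and analysis rules that follow from a stop are in other sections. Section 8.1 gives a participant who discontinues before Week 48 an ET Visit and a follow-up visit 4 weeks later. Section 8.5.1.1 says "liver biopsy will be performed at ET Visit if the participant has completed at least Week 20" and has not already had the Week 24 biopsy. Before Week 20, biopsy is only something to consider, and that sentence is worded for people leaving the study. A missing biopsy counts as nonresponse in the primary analysis (Protocol 9.5.2.1, SAP 6.1.1).

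**The concern.** Section 8.3.9.1 takes its definition of abnormal liver tests from Section 8.5.3.1, so both passages concern the same event. One requires discontinuation and the other allows interruption with a conditional restart. Separately, the general interruption rules in Section 8.4.6 contain neither the condition on cause nor an exception for liver tests, and Section 8.3.9.1 directs the reader to them.

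The first stake is safety and consistency. Two sites with identical cases could act differently, and a site relying on Section 8.4.6 alone could resume dosing in a participant whose liver-test elevation is unexplained, which Section 8.5.3.1 does not allow. The second is data handling. Exposure, the percentage of treatment completed (SAP 8.1), the count of AEs leading to discontinuation of treatment (SAP 6.2.1) and, for events before Week 20, biopsy availability all depend on how the event was classified.

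**Working it through.** **1. The passages side by side.** Take an illustrative case. At Week 12, aminotransferases are above 2 times Baseline and above 3 times the upper limit of normal, with an INR rise above 0.2, which is the first scenario in Section 8.5.3.1. All values are back at Baseline by Week 15.

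| Section | Other cause established | No other cause found |
|---|---|---|
| 8.3.9.1 | Discontinue; no restart route given | Discontinue; no restart route given |
| 8.5.3.1 | Restart allowed | Restart not allowed |
| 8.4.6.2 | Further dosing allowed | Further dosing allowed |
| 8.4.6.1 (if recorded as an AE) | Restart allowed after medical monitor consultation | Restart allowed after medical monitor consultation |

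In the first column, Section 8.3.9.1 stands against the other three. In the second, Sections 8.3.9.1 and 8.5.3.1 both leave the participant off drug, and only the general rules in 8.4.6 differ. Each situation is therefore a two-way conflict, and the source of the conflict differs between them.

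Section 8.4.6.1 does reach liver cases, because Section 8.5.3.1 requires a laboratory abnormality that interrupts dosing to be recorded as an AE or serious AE.

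**2. Route to the primary endpoint.** Handled as discontinued at Week 12, the participant goes to an ET Visit with no required biopsy. If none is taken, the outcome is nonresponse. Handled as interrupted and restarted, the participant stays on the Week 24 biopsy schedule, and a biopsy delayed to between Weeks 24 and 48 is still counted (SAP 7.2). From Week 20, a biopsy at ET is specified, so mainly its timing and the exposure differ.

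**3. Size per participant.** The final number randomized is 197, about 49 per arm. One response lost moves an arm's rate by 1/49 = 2.0 percentage points. In the Week 24 analysis of about 160 (SAP 7.2), with about 40 per arm, it is 1/40 = 2.5. Both are ceilings, reached only if the participant would have responded. At the planning response rates of 15% to 40%, the expected shift with 49 per arm is 0.15 × 2.04 = 0.3 to 0.40 × 2.04 = 0.8 points.

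**4. Power, as illustration only.** The plan gives no figure for liver-related stops. Its nearest design figure is at least 80% power for the Cochran-Armitage test (Protocol 9.1). With 40 per arm, rates 15/20/30/40%, scores 0 to 3 and one-sided 0.05:

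- Expected trend statistic: 40 × (−1.5×0.15 − 0.5×0.20 + 0.5×0.30 + 1.5×0.40) = 17.0
- Null SD: √(0.2625 × 0.7375 × 200) = 6.22
- SD under the alternative: √36.775 = 6.06
- Power: Φ[(17.0 − 1.645 × 6.22)/6.06] = 86.8% (simulation 87.2%)

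The stated figure is reproduced and is not disputed. The table assumes that a share of responders is lost through stops without biopsy.

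| Assumed loss | Active arms only, N=160 | All four arms, N=160 | Active arms only, N=197 |
|---|---|---|---|
| 1% | 86.0% | 86.3% | 91.6% |
| 2% | 85.1% | 85.9% | 91.0% |
| 5% | 82.4% | 84.6% | 88.8% |
| 10% | 77.3% | 82.1% | 84.4% |

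The documents do not say where in this range, if anywhere, the trial would fall.

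**The case against.** The strongest reply is that a specific rule narrows a general one. Section 8.5.3.1 sets exact thresholds and states its restart conditions as exclusive. Section 8.4.6.2 only says that dosing may resume and never names liver tests. A site can comply with both by following the stricter, and this is a reasonable reading. It stands as mitigation for the case with no other cause found. It does not settle the other case, because Section 8.3.9.1 is also about liver tests and cites Section 8.5.3.1 for its definition.

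A second reply is that the liver-test bullet in 8.3.9.1 refers only to the plain discontinuation rules in 8.5.3.1 (persistent elevation with symptoms, or close observation not possible). That is possible, but the bullet does not limit itself in this way. The list also contains a discretionary item, weight loss above 10%, so it is not uniformly mandatory. Equally, it spells out discretion there and not for liver tests.

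A third reply is medical monitor involvement: consultation in 8.4.6.1, notification in 8.4.6.2 and contact within 48 to 72 hours in 8.5.3.1. A reader might infer that Section 8.4.6.2 leaves a participant free to restart, and the documents do not support that. The contacts lower the risk of unexamined re-exposure. They do not remove the inconsistency, because the monitor works from the same text.

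Finally, the route to the endpoint has several steps, the biopsy and nonresponder rules apply to any early stop, and a completer analysis is planned. All of that is correct, and it is why the endpoint effect is secondary.

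**Conclusion.** The inconsistency is real and should be resolved. When another cause is established, Section 8.3.9.1 conflicts with Section 8.5.3.1. When none is found, Section 8.4.6, read alone, permits a restart that Section 8.5.3.1 does not. No section states precedence. The importance rests on participant safety and uniform handling, not on effect size.

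Three stronger readings are tempting and are not supported:

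- **Three incompatible outcomes for one participant.** Within either situation there are only two: off drug, or eligible to resume.
- **Permanent stopping under 8.3.9.1.** The liver-test bullet does not use that word. It is inferred from the mandatory wording, the ET Visit and the absence of a restart route.
- **A demonstrated distortion of the primary result.** The documents give no event rate. The ceiling is about 2 percentage points per participant in one arm of 49 (2.5 with 40), and it assumes an event before Week 20, handling as a discontinuation, no biopsy taken, and a participant who would otherwise have responded.

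**What to change.** Reconcile Sections 8.3.9.1, 8.4.6.1, 8.4.6.2 and 8.5.3.1 so that one consistent rule applies to liver-test events, or state an order of precedence among them. In the same text, make clear how the ET Visit and the biopsy schedule follow from whichever classification applies, so that exposure, discontinuation counts and biopsy availability are handled alike at every site. No view is taken here on which stopping, restart or ET rule is right; that is for the sponsor's clinical and safety team. The cost is a few sentences in a protocol amendment or administrative letter. The reconciliation itself requires no new assessments and no change to the analysis methods.
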